30 freshly extracted permanent teeth with MIH will be collected from the pediatric clinics of the University of Texas Health San Antonio (UTHSA). These teeth were extracted as part of the patient's standard of care and

donation will be done based on the patients willingness. If the patient wishes to donate the teeth, they will be placed in a container within the pediatric dental clinics and will be donated without identifiable information attached to them. The teeth will be cleaned of debris/stains and examined with a transilluminator. Teeth with MIH but free of caries or other malformations will be selected and cleaned with pumice to remove the pellicle. Using a water-cooled diamond wire saw, 3 blocks, two from MIH affected area and one from a healthy area will be produced from each tooth, with each block measuring approximately 2 mm length x 2 mm width x 1 mm thickness. The cut will take place so that the different layers from the outer surface to the inner surface present in each block are: outer enamel surface, enamel, dentino-enamel junction (DEJ) and dentin.

Measurement of baseline mineral density of the tooth blocks

Micro computed X-ray tomography (μ -CT) is a high resolution, non-destructive radiographic method of analysis that generates qualitative images and quantitative analysis of the mineral density (MD) in tooth samples. For this reason, images will be collected from the samples to measure the mineral density of the MIH enamel lesions before (MD_b) and after (MD_t) remineralization treatment as well as the mineral density (MDs) of healthy enamel samples. The μ -CT scanning and analysis procedure will be performed as described in our previous publications.¹⁷

Study Population/Participants

Fifteen subjects (8 females, 7 males) will be recruited into the study. The subjects to be included should be 18 to 60 years old in good general health with no known history of allergy to personal care/consumer products. They must have a minimum of 20 natural uncrowned teeth (excluding third molars), no active unrestored cavities and a normal salivary flow rate (stimulated and unstimulated flow of ≥ 0.7 ml/min and ≥ 0.2 ml/min respectively) ascertained from a preliminary sialometry test. They also should give written informed consent, be available throughout entire study, and be willing to wear intra-oral appliance 24 hours per day and use only assigned products for oral hygiene throughout the duration of the study.

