The 3 blocks from each tooth will be used, as follows: two blocks with MIH lesions will be used for remineralization assessment and one healthy tooth block will serve as control for the MD of healthy enamel. The MIH-bearing blocks will be covered with polyester gauze (Bard Peripheral Vascular, Inc., USA), which will facilitate plaque retention on the surface of the tooth blocks on intra-oral exposure. Following recruitment, an impression of the subject's lower dentition will be taken using an alginate impression material. A dental technician will fabricate a lower removable intra-oral appliance. Each of the MIH-lesion-bearing blocks will be mounted on each side within the acrylic portion of the removable appliance, using Intermediate Restorative Material (IRM) cement (fluoride-free). All appliances are sterilized with ethylene oxide prior to delivery to the subject.

Test Product Description and Labeling

The toothpastes to be used for treatments are 10% HAP toothpaste, 1450 ppm NaF fluoride toothpaste, and non-fluoride toothpaste (washout). The 2 test products will be coded by the manufacturing/packaging company, who will retain the code until the completion of the study and data interpretation. The experiment will consist of two distinct treatment phases, Phase 1 and Phase 2, during which subjects will be exposed to one of the 2 products in a randomized crossover design, with each phase lasting for 2 weeks.

Study Procedure and Patient Instructions

Prior to each 2-week treatment phase, subjects will complete a 1-week washout period. This period allows for attenuation of any residual effect of the subject's previously used toothpaste. During this period, no appliance will be worn, and subjects will be using only the provided washout toothpaste and a soft-bristled toothbrush twice daily. Following the washout period, the intra-oral appliance will be fitted to each subject by a qualified dentist. Immediately after fitting of the first appliance (on day 1 of the first treatment phase), each subject will receive a soft bristled manual toothbrush for use throughout the duration of the study and a toothpaste according to the treatment phase. They will make the first use of the test product under the supervision of the study coordinator. For the remainder of the study, subjects will complete the procedure at home and as instructed.

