The subjects will be instructed to brush their teeth with the appliance in the mouth, two times daily, for 3 minutes on each brushing episode, in the morning after breakfast and last thing before bed, then rinsing with 10 ml of water. In dispensing the toothpaste onto the toothbrush, the subjects should fill the toothbrush surface from end to end but no more than one ribbon of toothpaste. The subjects will be advised not to brush directly on the blocks but rather to brush around the blocks to prevent disruption of the plaque. Subjects should neither eat nor take any drink for at least 30 minutes after brushing, they will be also instructed to remove the appliance while eating. A timer and measuring cup will be provided to each subject. To monitor product usage and compliance, a diary will be provided to each subject and checked at every visit, to record the number of tooth-brushings performed each day and the time it was done. Further, subjects will be instructed to return the remaining washout or test toothpaste after each treatment phase. The weight of toothpaste will be measured before and after each treatment phase. Over the study period, all subjects are to maintain their normal dietary habits.

On day 15, the subject, without using the product that morning, will arrive at the clinic, and the tooth block will be harvested and sent to the laboratory for μ CT analysis. Then the subject will be given washout toothpaste and a soft-bristle toothbrush to undergo another 7-day washout period without an appliance. After completion of the second washout period, subjects will return to the clinic, and the appliance, with another MIH-bearing tooth blocks mounted, will be fitted to the subject for the phase 2 treatment period. This procedure will then be repeated until the 2-week treatment phase is completed, and each subject has gone through the two arms of the study.

Upon completion of the treatment phases, the post-remineralization mineral density (MDt) of all the MIH-lesion-bearing blocks exposed intra-orally for remineralization will be assessed with μ CT. For the lesion-bearing blocks,

this process will yield the following information: the pre-test (MD_b) and post-test (MD_t) mineral density of the lesions and their associated images, while for the healthy tooth blocks, the MDs and the μ CT images.

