At every visit, the dental examiner will visually examine the soft and hard tissues of the oral cavity and peri-oral area using a dental light and dental mirror. Additionally, subjects will be asked about and examined for any adverse events. Subjects may call and request a visit for any concern of potential adverse event.

Data Handling

Using the μ CT images, the pattern and the extent of remineralization produced within each lesion by each treatment product will be examined and described. This will be clearly shown by comparing the pre- and post-test images side-by-side. For all calculations, the absolute MD will be measured and used. For the remineralization blocks, the values of the MD_b and MD_t for each test product will be compared using paired t-test to determine any significant change (remineralization) made by the test product (intra-group comparison). However, to make comparisons between the two products (intergroup comparison), percentage change in MD calculated relative to the control will be determined for each test product as such: % Change in MD (% Δ MD) = [(MD_b – MD_t)/MD_b] x 100

The percentage MD recovery following remineralization will be calculated as follows:

% MD recovery (%MDR) = [(B-T)/(B-S)] x 100, with S = mean MDs of healthy enamel blocks, B = mean MD_b of MIH enamel blocks before remineralization, and T = mean MD_t of MIH enamel blocks after intra-oral exposure.

Sample Size Calculation

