The power analysis and sample size calculation were performed using nQuery Advisor software (Statistical Solutions, Cork, Ireland). The sample size for this study is based on the primary efficacy parameter, % MDR following 2 weeks of treatment. A sufficient number of subjects will be screened to randomize approximately 15 subjects with the intention that approximately 15 subjects complete all study treatments and be evaluable for the efficacy analysis. With these conditions met, the study will have 80% power at the 5% significance level, using two-sided testing, to detect a mean treatment difference in %MDR of approximately 8.1% assuming a within subject standard deviation of approximately 12.6%. In the absence of available 2 week data from previous mineral density studies, the within subject standard deviation has been estimated using 14-day post-treatment data from a previous results obtained by this group in a demineralization and remineralization study using HAP toothpaste¹⁵. In that study the mean % change in mineral loss was equal to 30.3 with a standard deviation equal to 16.3.

Statistical Analysis

After assumptions of normality and homogeneity of variances have been verified by normal probability plots, comparisons of the mean values of MD, %ΔMD and %MDR between the two treatment groups as well as the intra-group comparisons will be performed using the paired Student's t-test (STATA version 10.0, StataCorp LP, USA) at a significance level of 5%. The primary endpoints of the present study are expected to be enhanced remineralization of MIH lesion.

E. References

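### The within-product before-after t-test is described on blocks, two per mouth, with no averaging or cluster term; if their changes are positively correlated, its true error rate exceeds 5%

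*Combined protocol and SAP*

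**What the plan says.** All references are to Section D of the combined protocol and SAP.

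- **Specimens** (Production of Samples): "30 freshly extracted permanent teeth with MIH will be collected", and "3 blocks, two from MIH affected area and one from a healthy area will be produced from each tooth".
- **Subjects** (Study Population/Participants): "Fifteen subjects (8 females, 7 males) will be recruited into the study". Each goes through both phases.
- **Appliance** (Construction of the in-situ appliance): "Each of the MIH-lesion-bearing blocks will be mounted on each side within the acrylic portion of the removable appliance".
- **Before-after test** (Data Handling): "For the remineralization blocks, the values of the MD_b and MD_t for each test product will be compared using paired t-test". No n or degrees of freedom are given, and nothing is said about how two blocks from one mouth enter the test.
- **Averaging** (Data Handling): means over blocks appear only in the definition of percentage recovery (%MDR), which does not say whether the mean is taken per subject or per treatment group.
- **Method** (Statistical Analysis): the paired Student's t-test at 5% is the only test named, for comparisons both within and between products.
- **Planning unit** (Sample Size Calculation): "A sufficient number of subjects will be screened to randomize approximately 15 subjects". The count is in subjects.

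**The concern.** A paired t-test removes the dependence between the before and after readings of the same block. It does not remove dependence between the changes of two different blocks. Two blocks worn in one appliance over the same two weeks share saliva, brushing, diet and wearing time, so their changes may well move together. If they enter as separate pairs, the test counts 30 independent observations where there are fewer. The standard error is then too small and the p-value too low.

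This is the test the plan uses to decide whether a product produced a significant change in mineral density, so an inflated error rate would make a claim of remineralization easier to reach than the stated 5% level implies.

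**Working it through.** **Step 1. Count the blocks.** The plan states no n for this test, so there is no figure of its own to reproduce. The power figure under Sample Size Calculation concerns a between-product difference in %MDR and is not used here. The count follows from the inputs above:

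- Supply: 30 teeth × 2 MIH blocks = 60 blocks.
- Use: 15 subjects × 2 phases × 2 sides = 60 blocks.

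The two agree. Each product therefore has 60 / 2 = 30 blocks in 15 mouths, two per mouth. The total also fits if each subject receives two teeth and each tooth gives one block to each phase. Either way, an appliance holds two blocks.

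**Step 2. Effect on the standard error.** Let each block's change have variance σ², and let ρ be the correlation between the changes of the two blocks in one mouth (the ICC).

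- True variance of the mean of 30 changes: σ²(1 + ρ)/30.
- Variance assumed by a 30-pair t-test: about σ²/30.
- The standard error is too small by a factor √(1 + ρ), and the effective number of blocks is 30/(1 + ρ).

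**Step 3. Effect on the error rate.** The normal approximation is 2 × [1 − Φ(1.96/√(1 + ρ))]. At ρ = 0.5, for example, 1.96/1.225 = 1.600, which gives 11.0%. As a check, 200,000 null trials were simulated at each ρ, with 15 subjects × 2 blocks. Each was tested on 30 pairs (29 df) and on 15 subject means (14 df).

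| ρ (assumed) | √(1 + ρ) | Effective blocks | Approximation | 30 pairs, simulated | 15 means, simulated |
|---|---|---|---|---|---|
| 0 | 1.00 | 30.0 | 5.0% | 5.0% | 4.9% |
| 0.1 | 1.05 | 27.3 | 6.2% | 6.1% | 4.9% |
| 0.3 | 1.14 | 23.1 | 8.6% | 8.5% | 5.0% |
| 0.5 | 1.22 | 20.0 | 11.0% | 11.1% | 5.0% |
| 0.8 | 1.34 | 16.7 | 14.4% | 15.2% | 5.0% |
| 1.0 | 1.41 | 15.0 | 16.6% | 17.7% | 5.0% |

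**Step 4. Exact check at ρ = 1.** Every value is then duplicated, and the 30-pair statistic equals the correct 15-value statistic times √(2 × 29/28) = 1.439. It is compared with 2.045 (29 df), so the test rejects when the correct statistic exceeds 2.045/1.439 = 1.421. With 14 df the two-sided probability is 17.7%, which matches the simulation. The normal approximation runs low at high ρ because it ignores the loss of degrees of freedom.

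**The case against.** The best reply is that the plan leaves the unit unstated and so commits no error. The reference to blocks may only separate the treated specimens from the healthy control block. The sample size is in subjects, and the %MDR definition shows that some averaging is intended. This stands in part: averaging is not ruled out, and a reader who infers that the plan has fixed on 30 independent pairs goes further than the text. But no sentence calls for averaging in this test, and an analyst following the wording would enter blocks.

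The block count can also be questioned. Study Procedure and Patient Instructions says that "the tooth block will be harvested and sent to the laboratory", in the singular, and then that "the appliance, with another MIH-bearing tooth blocks mounted, will be fitted to the subject for the phase 2 treatment period". The wording is mixed, but the appliance section and the total of 60 favour two per appliance.

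Three stronger readings are tempting and are not supported:

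- **Both blocks in an appliance come from one tooth.** This is plausible but not stated. Nor would it show a high ρ by itself, since a stable difference in density between teeth cancels in the before-after change.
- **The error rate roughly doubles.** That needs ρ of about 0.4 to 0.5 (simulated 9.9% and 11.1%). The documents give no correlation, and over ρ from 0 to 1 the inflation runs from none to about 3.5 times (17.7/5).
- **The same inflation reaches the primary comparison.** The sample size rests on %MDR compared between products. Subject effects common to both phases cancel there if they are additive. Effects specific to a subject's phase do not, so some dependence could remain, but the figures above do not measure it.

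**Conclusion.** The point holds in conditional form. Taken literally, the within-product test uses 30 block pairs from 15 mouths per product with no allowance for clustering, and it is anti-conservative at any positive correlation between the changes of two blocks in a mouth. The size depends on a correlation that the documents do not supply, so only the range in the table can be defended, from no inflation at ρ = 0 to about 18% at ρ = 1.

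The conclusion rests on two blocks per appliance, which the counts support, and on blocks being entered singly, which is the literal reading though no n confirms it. It does not rest on same-tooth placement. Its reach is also limited: effectiveness is to be declared on a 20% recovery criterion (Specific Aims), and the primary parameter is %MDR. It should be corrected before the data are analysed, but it does not undermine the design.

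**What to change.** In Data Handling and in Statistical Analysis, state that MD_b, MD_t and the derived measures are averaged over the two blocks within each subject and phase, and that all paired tests, within and between products, use the 15 subject values (14 df). Say also at which level the means in the %MDR formula are taken.

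A mixed model on block values with random effects for subject and subject-by-phase is an alternative, but not an exact equivalent: fitted to both products it may pool variance across them and change the degrees of freedom. If it is preferred, it should be specified in advance.

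The cost is a few sentences and no new data. The downside is a wider confidence interval for the within-product change. Relative to the 30-pair interval, the width grows by about (2.145/2.045) × √(1 + ρ): 1.05 times at ρ = 0 and 1.28 times at ρ = 0.5. Only the 1.05 is a real cost of averaging, and it would arise even if the blocks were independent; the rest corrects an interval that was too narrow.

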MIH is a qualitative enamel defect observed on at least one first permanent molar (FPM) with or without affecting permanent maxillary incisors¹. Clinically, it's diagnosed when a FPM presents with a demarcated opacity, larger than 1 mm, varying in color from white to yellow and even brown^{2,3}. Additionally, post-eruptive enamel breakdown, atypically sized, shaped, and extended restorations, or a history of extraction of FPMs in an otherwise sound dentition, are also diagnostic criteria of MIH. The location, asymmetry and varying severity of the defects, distinguishes them from other enamel mineralization defects such as fluorosis⁴. The severity of the affection can be divided into 2 categories, mild and moderate/severe. These categories are differentiated clinically by the presence or absence of enamel breakdown, the degree of hypersensitivity and the esthetic concerns³. It is also correlated with reduced levels of mineral density (MD) of the affected enamel to 2.24 g/m³ in mild cases and 1.93 g/m³ in moderate/severe cases in comparison to a 2.51 g/m³ average MD of normal enamel⁵.

Hypomineralization can affect both primary and permanent teeth, but the molar-incisor model is the most common with a reported prevalence between 10% to 20%^{6,7}. As for their etiology, MIH defects can result from genetic or systemic environmental factors. Perinatal and postnatal factors appear to be the most strongly associated with its occurrence⁸. In fact, premature birth and associated complications, hypoxia, dioxin exposure and other childhood illnesses such as ear or respiratory infections and antibiotic use are implicated in an increased incidence of MIH. If these conditions develop in the early childhood, up to age 3, when the crowns of the FPMs and incisors are

undergoing mineralization, they predispose the child to MIH^{3,9}. Consequently, the time of onset, span and severity of the conditions dictate the pattern and intensity of the lesions.

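### The printed %ΔMD formula turns every mineral gain negative, and its baseline denominator does not match the stated comparison with the control

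*Combined protocol and SAP*

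**What the plan says.** All places are in the combined protocol and SAP, mostly under D. Experimental Design.

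- **Symbols.** The section on measuring baseline mineral density says that scans will give "the mineral density of the MIH enamel lesions before (MD_b) and after (MD_t) remineralization treatment". It uses MDs for healthy enamel.
- **%ΔMD.** For the between-product comparison, Data Handling says that "percentage change in MD calculated relative to the control will be determined for each test product". It then prints a formula that, after its opening brackets, reads "MD_b – MD_t)/MD_b] x 100".
- **Control.** In the section on constructing the appliance, "one healthy tooth block will serve as control for the MD of healthy enamel".
- **%MDR.** Data Handling defines it as [(B-T)/(B-S)] x 100, "with S = mean MDs of healthy enamel blocks, B = mean MD_b of MIH enamel blocks before remineralization", and T as the corresponding mean after intra-oral exposure.
- **Use.** Statistical Analysis compares MD, %ΔMD and %MDR between products by paired t-test. Sample Size Calculation names %MDR as the primary parameter and bases the sample size on it.

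**The concern.** Two things do not fit together in the definition of %ΔMD.

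First, the numerator is before minus after. That order would suit a measure of mineral loss. Here the quantity is density and the hoped-for result is an increase, so success is printed as a negative percentage. %MDR, defined a few lines later, is positive for the same success. A report that follows both formulas exactly would show the better product lower on one measure and higher on the other.

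Second, the lead-in and the formula name different reference quantities. The plan uses *control*, when speaking of blocks, for the healthy one, yet the formula divides by the lesion's own starting density. The choice changes the size of %ΔMD, and changes it more for severe lesions than for mild ones.

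At stake are the stated direction and size of the measure that Data Handling introduces for comparing the products.

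**Working it through.** **Inputs.** From Significance / Background: mild lesions 2.24, and "1.93 g/m³ in moderate/severe cases in comparison to a 2.51 g/m³ average MD of normal enamel". Units cancel in the ratios. The illustration uses recovery of 20% of the deficit, because 20% is the threshold in Specific Aims. The plan gives no worked value of %ΔMD to reproduce, so both printed formulas are evaluated directly.

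**Step 1: one lesion, 20% of the deficit recovered.**

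| | Mild | Moderate/severe |
|---|---|---|
| Before (B) | 2.24 | 1.93 |
| Deficit, S - B with S = 2.51 | 0.27 | 0.58 |
| Gain, 20% of the deficit | 0.054 | 0.116 |
| After (T) | 2.294 | 2.046 |
| %MDR = (B-T)/(B-S) x 100 | -0.054/-0.27 = +20% | -0.116/-0.58 = +20% |
| %ΔMD as printed = (B-T)/B x 100 | -0.054/2.24 = -2.41% | -0.116/1.93 = -6.01% |
| Numerator reversed, over baseline | +2.41% | +6.01% |
| Numerator reversed, over healthy MD | 0.054/2.51 = +2.15% | 0.116/2.51 = +4.62% |

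In %MDR the numerator and the denominator are both negative for a gain, so the signs cancel. In %ΔMD only the numerator is negative.

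**Step 2: two products.** Take one product at 20% recovery and the other at 11.9%, which is the 8.1-point %MDR difference in Sample Size Calculation, with the same baseline for both.

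- Mild: printed %ΔMD is -2.41% against -0.119 x 0.27/2.24 = -1.43%. The difference is -0.081 x 0.27/2.24 = -0.98 points.
- Moderate/severe: -6.01% against -0.119 x 0.58/1.93 = -3.58%. The difference is -0.081 x 0.58/1.93 = -2.43 points.

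An advantage of +8.1 points on %MDR thus appears as a negative difference on %ΔMD.

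**Step 3: the denominator.** The same absolute gain of 0.054 is 0.054/2.24 = 2.41% of a mild baseline and 0.054/1.93 = 2.80% of a severe one, but 0.054/2.51 = 2.15% of healthy density for both. Dividing by baseline instead of healthy MD enlarges the value by 2.51/2.24 = 1.12 (mild) or 2.51/1.93 = 1.30 (severe).

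**Step 4: effect of the sign on the test.** Negating every %ΔMD negates each paired difference and leaves the standard deviation of the differences unchanged. The t statistic changes sign and the two-sided p-value stays the same. In 15 simulated pairs, t was -1.423 one way and +1.423 the other, with p = 0.177 both times.

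**The case against.** The strongest reply is that this is a slip on a measure that does not carry the trial. The primary parameter, %MDR, is correctly signed. Two-sided p-values do not move. Data Handling also tests absolute density before against after within each product and compares the scan images, so a reader can see which way density moved. All of that stands, and it limits the weight of the point. It does not make the printed definition right: means, confidence limits and the stated direction of %ΔMD would still be reversed.

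On the denominator, it is fair to say that the explicit formula outranks a loose lead-in, and that the healthy block is described only as the control for healthy density, which is the part S plays in %MDR. That is a good reason to follow the printed denominator by default. The wording still needs to agree with it.

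Some stronger readings are tempting, but the documents do not support them.

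- *The trial could name the wrong product as better.* The primary measure and the absolute densities keep the right direction.
- *%MDR cannot be tested.* Read literally, means over blocks give one value per product. But the planned paired t-test, the within-subject standard deviation and the 15 evaluable subjects already imply one value per subject and product. This is missing detail, not an error.
- *The number of lesion blocks per phase is contradictory and invalidates the measure.* One section says "Each of the MIH-lesion-bearing blocks will be mounted on each side within the acrylic portion of the removable appliance" and another that "the tooth block will be harvested and sent to the laboratory". The wording is loose, but block totals cannot settle it: teeth are selected from the 30 collected, so the number of usable blocks is not stated. The sign and denominator points do not depend on it.
- *The choice of healthy reference S biases the comparison.* The documents give no figure from which to size such an effect.

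**Conclusion.** The point holds, with limited reach. The sign error follows directly from the plan's own definitions and needs no assumption beyond a density gain. The mismatch between the control wording and the baseline denominator is also plain from the text, although the documents do not say outright which the authors intended.

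The sizes are illustrative. At 20% recovery with the Background densities, printed %ΔMD is -2.41% (mild) or -6.01% (moderate/severe) where %MDR is +20%. The two-product figures assume equal baselines for both products.

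The consequence is confined to the sign, direction and size of a non-primary measure. Correcting the sign does not affect %MDR, two-sided p-values, the sample size or the power. Changing the denominator is not a mere change of sign and could alter the %ΔMD test result, so that choice should be settled in advance.

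**What to change.** In Data Handling:

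1. Print %ΔMD = [(MD_t - MD_b)/MD_b] x 100 and describe it as change relative to baseline. This keeps the printed denominator.
2. If healthy enamel was the intended reference, keep the reversed numerator and the reference to the control, name that control as healthy enamel, and change the denominator to MDs. The examples then become 2.15% and 4.62%.
3. As a clarification only, state that %MDR is computed for each subject in each phase, with B and T taken over that subject's lesion block or blocks in that phase.

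The cost is a few lines of wording. No new measurement, subject or scan is needed. The choice between 1 and 2 should be recorded before the product codes are released.

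### Fifteen subjects do not give the stated 80% power for an 8.1-point %MDR difference: power is about 37% as written, or 64% on the kinder reading of the SD

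*Combined protocol and SAP*

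**What the plan says.** Section D of the combined protocol and SAP, under Sample Size Calculation, sizes the trial on %MDR after 2 weeks, which it names as the primary efficacy parameter. The plan is to "randomize approximately 15 subjects with the intention that approximately 15 subjects complete all study treatments and be evaluable for the efficacy analysis". On that basis "the study will have 80% power at the 5% significance level, using two-sided testing", and the target is "to detect a mean treatment difference in %MDR of approximately 8.1% assuming a within subject standard deviation of approximately 12.6" percent.

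The SD is attributed to a previous study by the same group, from which the plan reports only this: "In that study the mean % change in mineral loss was equal to 30.3 with a standard deviation equal to 16.3". No step from 16.3 to 12.6 is shown.

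Recruitment of Study Subjects describes a randomized crossover and codes the subjects CP01 to CP15. Statistical Analysis compares the two products with a paired t-test at 5%.

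**The concern.** In a two-period crossover, each subject's contrast is the difference of two measurements, so its SD is √2 times the within-subject SD. Taken as labelled, 12.6 gives a paired-difference SD well over twice the 8.1-point target. Fifteen pairs are too few for 80% power at that ratio.

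This paragraph is the only justification given for the sample size. Null hypothesis 2 is that the two toothpastes do not differ significantly. If the trial does not reject it, a reader who trusts the 80% will take the result as fair evidence of similarity. No confidence interval or equivalence margin is planned that would check that reading.

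**Working it through.** **Inputs (Sample Size Calculation and Statistical Analysis).** n = 15 evaluable subjects; difference δ = 8.1; SD 12.6, labelled within-subject; two-sided α = 0.05; paired t-test; one value per subject per product.

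**Method.** The noncentrality parameter is λ = δ / (SD_diff/√n). Power is the probability that a noncentral t with n − 1 degrees of freedom and noncentrality λ falls beyond the two-sided 5% critical value (2.145 for 14 df).

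**Attempt to reproduce 80% as written.**
- SD_diff = 12.6 × √2 = 17.82
- Standard error = 17.82/√15 = 4.60
- λ = 8.1/4.60 = 1.76
- Power = **37.5%** (37.1% with the n − 2 df of a 2×2 crossover analysis; 42.1% by normal approximation; 37.7% by simulation)

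**12.6 read as the SD of the paired differences.**
- Standard error = 12.6/√15 = 3.25
- λ = 8.1/3.25 = 2.49
- Power = **63.9%** (63.4% with n − 2 df; 70.2% by normal approximation; 64.0% by simulation)

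**Difference detectable at 80% power with n = 15.** With 14 df this is about 3.013 standard errors.
- 3.013 × 4.60 = 13.9 points (12.6 as within-subject SD)
- 3.013 × 3.25 = 9.8 points (12.6 as SD of differences)

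**Subjects needed for 8.1 points at 80%.**

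| Reading of 12.6 | SD_diff | Power at n = 15 | Detectable difference at n = 15 | N for 80% |
|---|---|---|---|---|
| Within-subject SD (as labelled) | 17.82 | 37.5% | 13.9 | 40 (80.05%; n = 39 gives 79.0%) |
| SD of paired differences | 12.6 | 63.9% | 9.8 | 21 (80.0%; n = 20 gives 77.9%) |

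**Rounding.** Varying 8.1 over 8.05 to 8.15 and 12.6 over 12.55 to 12.65 gives power of 36.8% to 38.1% on the first reading and 63.1% to 64.8% on the second. Rounding does not explain the gap.

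**What would make 80% true at n = 15.** SD_diff = 8.1 × √15/3.013 = 10.4, that is, a within-subject SD of 10.4/√2 = 7.4.

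**The cited SD.** If 16.3 were used directly, power at n = 15 would be 43.4% (as SD of differences) or 24.5% (as within-subject SD, SD_diff = 23.05; detectable difference 3.013 × 23.05/√15 = 17.9 points). If 16.3 is the total SD of a single measurement on the same scale, which is an assumption, then reaching 12.6 implies a within-subject correlation of 1 − (12.6/16.3)² = 0.40. The plan gives no such correlation.

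**Possible origins.** With within-subject SD 12.6, the detectable difference at n = 40 is 8.09, matching the stated 8.1. Alternatively, a one-sided 5% normal approximation with 12.6 as the SD of differences gives n = (1.645 + 0.842)² × (12.6/8.1)² = 14.96. The documents establish neither.

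**The case against.** The strongest counter-argument concerns the number of blocks. Thirty teeth with two MIH blocks each make 60 blocks, which equals 15 subjects × 2 phases × 2 blocks, and the appliance carries a block on each side. If two blocks per phase were averaged, were independent, and 12.6 were a block-level SD of paired differences, SD_diff would be 12.6/√2 = 8.9 and power about 91%. So 64% is not a ceiling over every conceivable design. But this needs assumptions the plan does not state, departs from its within-subject label, and yields about 91% rather than 80%. If 12.6 is instead a block-level within-subject SD, averaging two independent blocks gives SD_diff = 17.82/√2 = 12.6 and 64% again. The text is also unclear on the number of blocks, since Study Procedure speaks of harvesting a single block on day 15.

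The one-sided normal approximation does land on 15, but the plan specifies testing "at the 5% significance level, using two-sided testing". Even the two-sided normal approximation reaches only 70%.

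Three smaller points are fair. The match at N = 40 does not prove where the figures came from. The 0.40 correlation depends on what 16.3 measures, and it is described as the SD of a different outcome. And the plan nowhere says that a non-significant result will be read as equivalence; that is a foreseeable misreading, not a stated intention. None of these restores the 80%.

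**Conclusion.** The concern holds. The stated 80% power does not follow from the stated inputs. With 15 evaluable subjects and the planned two-sided paired t-test, power for 8.1 points is about 37% as written and 64% if 12.6 is the SD of the paired differences; the corresponding chance of missing that difference is 63% or 36%. This assumes one value per subject per product and full completion by all 15; any loss lowers power further. Within the two readings of 12.6 that the paragraph can bear, 64% is the upper limit. The missing derivation of 12.6 is a separate gap that compounds the problem. The error concerns the between-product comparison; it says nothing about power for the 20% recovery criterion in the Specific Aims.

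**What to change.** Keep 15 subjects and replace the power statement with one that the design supports, for example:

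*With 15 evaluable subjects and a within-subject SD of 12.6 percentage points (SD of the paired difference 17.8), a two-sided 5% paired t-test has 80% power to detect a %MDR difference of about 13.9 points; power for 8.1 points is about 37%.*

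If 12.6 is in fact the SD of paired differences, say so and state 9.8 points and 64% instead. In either case:
- Show how 12.6 was obtained from the earlier study's 16.3, including any correlation assumed, and why an SD for change in mineral loss carries over to %MDR.
- In Statistical Analysis, report the between-product difference with its 95% confidence interval, and state that non-significance will not be read as equal effectiveness.

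The cost is wording only, with no extra subjects or visits, though the stated sensitivity becomes less favourable. If 80% power for 8.1 points is essential, the alternative is 40 subjects (or 21 if 12.6 is the SD of differences), which would be a substantive change to the trial.
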